10 PHARMACOKINETIC ANALYSES

Standard non-compartmental approaches using Phoenix WinNonlin (Pharsight Corporation, Princeton, NJ, USA; Version 7.0 or higher) will be used to estimate PK parameters in serum and from nasopharyngeal secretions as described below. All calculations will use the actual times recorded in the EDC system for dosing and sampling. Individual and mean (\pm SD) or median concentrations versus time profiles will be plotted on both linear and logarithmic scales. Additional plots and PK parameters may be generated as appropriate.

The following PK parameters will be determined for VIS410 in serum (all subjects) and/or from nasopharyngeal secretions (only in the first 50 subjects enrolled):

- C_{\max} : maximum observed concentration
- T_{\max} : time of C_{\max}
- T_{last} : time of the last measurable concentration
- $AUC_{0-\infty}$: area under the concentration-time curve from time 0 extrapolated to infinity
- $AUC_{\% \text{extrap}}$: percent extrapolated to $AUC_{0-\infty}$
- $AUC_{0-\text{last}}$: area under the concentration-time curve from time 0 to the last measurable concentration
- $t_{1/2}$: terminal elimination half-life
- CL: total clearance (serum only)
- V_d : volume of distribution (serum only)
- Ratio of nasal: serum AUC in subjects with both values available

Additional PK parameters may be determined as appropriate.

A population PK analysis using mixed-effects modeling may be conducted to estimate the typical values and inter-patient variability of VIS410 PK parameters in serum and/or nasopharyngeal secretions and to assess the effect of covariates on model parameters. Data from this study may also be pooled with data from prior studies. If conducted, this analysis will be presented in a separate report outside the CSR.

10.1 Serum Pharmacokinetics

Serum concentrations and the computed PK parameters will be listed by treatment group and nominal time of collection. Summary statistics of serum concentrations and PK parameters will be presented by nominal time of collection including n, mean, geometric mean, standard deviation, CV, median, and ranges, as appropriate. Additional analyses and summaries may be generated as appropriate.

10.2 Nasopharyngeal Secretion Pharmacokinetics

Individual concentrations versus time profiles will be plotted on both linear and logarithmic scales in all subjects. Mean (\pm SD) or median concentrations versus time profiles will be plotted on both linear and logarithmic scales for the first 50 subjects enrolled that have the full PK profile collected. PK parameters listed above ([Section 11](#)) will be determined for VIS410 from nasopharyngeal secretions in the first 50 subjects enrolled only. Summary statistics of nasopharyngeal concentrations (first 50 subjects and in all subjects) and PK parameters (first 50 subjects only) will be presented by nominal time of collection including n, mean, geometric mean, standard deviation, CV, median and ranges, as appropriate. Additional analyses and summaries may be generated as appropriate.

Correlations between serum PK parameters and nasopharyngeal PK parameters will be presented. The 2 ratios of nasal AUC/serum AUC from the Day 3 visit until the last measurement and to infinity, will also be summarized with these statistics.

11 PHARMACODYNAMIC AND EXPLORATORY ANALYSES

11.1 Anti-influenza A Antibodies

Titer of anti-influenza A antibodies (H1 and H3 strains) will be summarized at Baseline/Day 1 and Day 28 with n, mean, SD, geometric mean, CV, minimum and maximum by visit and treatment group for the mITT population. Values below the limit of quantification (BLQ) will be listed as <BLQ and summarized as zero. Values that are <10 (LLOQ) will be assessed as 5 and values >10240 (ULOQ) will be assessed as 10240.

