Study Time Point	Screening ¹	Day 1					Clinic Visit Day						
		Baseline ¹	Pre-dose	0 hour	End of Infusion	≥2 Hours from End of Infusion	3 (±1) ²	5 (±1) ²	7 (±1)	14 (±3)	28 (±3)	56 (±7)	100 (±7) FU/ET ³
Screening/Administrative Assessments													
Informed consent	X												
Inclusion/exclusion criteria	X												
Medical history and demographics	X												
Admission		X											
Discharge						X							
Nasopharyngeal swab for Rapid flu test ⁴	X												
Onset of symptoms interview	X												
Randomization		X											
Safety Assessments ⁵													
Supine ECG ⁶	X				X								
Vital signs ⁷	X	X ⁸			X	X	X	X		X	X	X	X
Body temperature ⁹	X	X ⁸			X	X	X	X	X	X	X	X	X
Physical exam	X												
Targeted physical exam ¹⁰		X ⁸				X	X	X	X	X	X	X	X
Urine pregnancy test ¹¹	X												X
Serology (HIV rapid test) ¹²	X												
Chemistry ¹³	X							X		X			X

Study Time Point	Screening ¹	Day 1					Clinic Visit Day						
		Baseline ¹	Pre-dose	0 hour	End of Infusion	≥2 Hours from End of Infusion	3 (±1) ²	5 (±1) ²	7 (±1)	14 (±3)	28 (±3)	56 (±7)	100 (±7) FU/ET ³
Hematology ¹³	X							X		X			X
Urinalysis ¹³	X							X		X			X
Instructions conmeds and FluPRO	X												
Observation in unit				X	X	X							
FluPRO completion ¹⁴		X					X			X			
FluPRO compliance						X	X	X	X				
FluPRO collection, review and reinstructions							X	X	X				
AESIs		X									X		X ¹⁵
Concomitant therapy, AEs ²		X											X
Collection of SAEs		X											X
Influenza complications		X											X
Study Agent Administration/Virologic/PK, and Immunogenicity Assessments													
Pretreatment medications – 1 hour (±5 min) prior to start of infusion ¹⁶			X										
VIS410/placebo infusion ¹⁷				X									
Serum PK			X ¹⁸		X ¹⁹		X	X	X	X	X	X	X
Nasopharyngeal swab ²⁰			X ¹⁸				X	X	X	X ^{21, 22}	X ^{21,22}	X ^{21,22}	X ^{21,22}
Serum ADA			X							X		X	X
Serum HAI sample			X							X	X		

¹ Screening and baseline activities may be performed on the same day.

² Subjects will have a follow-up phone call in the evening of the dosing day to ensure subjects' safety and well-being. In addition, between clinic visits up to Day 7 (e.g., Days 2, 4 and 6), subjects will receive a follow-up telephone call to ensure compliance with FluPRO Influenza Symptom Questionnaire and review any new or worsening signs or symptoms.

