A total of 46 subjects were treated with VIS410 (n=33) or placebo (n=13) across 5 cohorts. Cohorts were performed sequentially and included different pretreatment regimens used to mitigate the GI events observed with VIS410. Preliminary findings from the first 31 subjects are presented below.

Preliminary Efficacy Data

A partially blinded pre-specified interim analysis of the first 3 cohorts was conducted to evaluate the safety and efficacy of the 2300 mg VIS410 dose and to determine whether dose escalation was appropriate. The distribution of subjects is presented in Table 3.

Table 3. Distribution of Subjects

Treatment	No. Dosed	Per Protocol*	No. Infected**
Placebo	13	9	7
VIS410 (2300 mg)	18	16	13
Total	31	25	20

HAI = hemagglutinin inhibition assay positive seroconversion at Day 14 or 28.

*Subjects with HAI >10 at baseline excluded per inclusion/exclusion criteria.

**Infected subjects who are either polymerase chain reaction positive or HAI positive.

Based on the preliminary results, VIS410 2300 mg dose demonstrated a statistically significant antiviral effect with a 76% and 91% reduction in nasopharyngeal viral AUC by

quantitative reverse transcriptase polymerase chain reaction (qRT-PCR) and half-maximal tissue culture infective dose (TCID₅₀) compared to placebo (Table 4).

Table 4. Viral Load and AUC Data

Viral Measure	Placebo (N=7)	VIS410 (N=13)	Reduction (%)	p Value*
Median Viral AUC TCID ₅₀ (log ₁₀ X hours)	546	45	92	0.019
Median Viral AUC qPCR (log ₁₀ X hours)	1031	235	77	0.024
Median Peak Viral Load TCID ₅₀ (log ₁₀)	5.0	2.7	2.2	0.009
Median Peak Viral Load qPCR (log ₁₀)	7.1	5.6	1.5	0.043

*Calculated with Mann-Whitney U Test.

In addition, analysis of the symptoms data demonstrated a trend in respiratory symptom resolution that was consistent with the virology data. Although this study was not powered to detect a statistical difference in symptom relief, a 2-day reduction in resolution of upper respiratory symptoms and AUC was observed in the VIS410 2300 mg group vs. placebo.

Preliminary Safety Data

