- Frequency tabulation of the occurrence and severity of each of the subject-reported symptoms of influenza-like illness by assessment time point and by treatment group
- Descriptive statistics of the duration of each of the subject-reported symptoms of influenza-like illness by treatment group

Additional sensitivity analysis may be conducted excluding subjects that received concomitant antiviral therapy during the course of the study. The mITT population will be used for the summaries. Additional populations may be analyzed as described in the SAP.

9.3.6 *Immunology*

Immunological assessments will be summarized by parameter, treatment group, and time point using descriptive statistics:

- Anti-VIS410 antibody titers by ADA in serum
- Anti-influenza A antibodies by HAI in serum
- HAI levels to determine a proper immune response to the influenza infection

The mITT population will be used for the summaries. Additional populations may be analyzed as described in the SAP.

Anti-Drug Antibodies

Anti-VIS410 antibody titer will be summarized by treatment group and by time point using descriptive statistics.

9.3.7 *Exploratory Pharmacokinetic/Pharmacodynamic Analyses*

Various techniques will be used to explore exposure-response relationships, and to compare the strength of the relationship between each independent variable (e.g., AUC, C_{max} , and concentration at specific time point) and the dependent variables (e.g., viral AUC, peak viral load, and time to cessation of viral shedding, clinical symptoms, and additional endpoints). These techniques may include graphical and statistical methods, including the creation of boxplots, spaghetti plots, histograms, and a variety of linear, nonlinear, or logistic regression techniques and time-to-event methods. If appropriate, continuous independent variables will be evaluated as such, and as categorical variables (grouping subjects into exposure categories).

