5.1.2 Modified Intent-to-Treat Population

The mITT population will include all subjects who receive IV study drug and are confirmed influenza A positive by a molecular test at the central virological laboratory.

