11.2 Nasopharyngeal Viral Load

Standard non-compartmental approaches using Phoenix WinNonlin (Pharsight Corporation, Princeton, NJ, USA; Version 7.0 or higher) will be used to calculate peak viral load (VL) and the area under the viral load-time curve (VL AUC). Viral load at each study visit, proportion of subjects with negative results at each study visit, peak VL, and VL AUC based on qRT-PCR and TCID₅₀ from nasopharyngeal secretions will be summarized with n, mean, SD, geometric mean, CV, minimum and maximum values in the mITT population overall and per influenza A virus subtype. All available viral data within the mITT population will be assessed to calculate proportion of subjects with negative results at each study visit. For all other calculated parameters, viral load will be assessed on all samples in the mITT population collected through the Day 7 visit. In addition, VL and VL AUC for the first 50 subjects will be listed through Day 14 (no summary statistics will be presented). For missing data on Day 3, Day 5 and Day 7, the analysis will be conducted without imputation and with the last observable measurement carried forward (LOCF). For missing data on Day 1, the analysis will be conducted by replacing the missing data with the Day 3 observable measurement. Subjects missing both Day 1 and Day 3 virology data will be removed from the analysis.

A t-test will be used to assess the difference between treatment groups in the VL AUC and peak VL from nasopharyngeal swabs based on qRT-PCR and TCID₅₀. If the assumptions needed for the t-test are not met, log transformation and/or non-parametric methods will be used.

Chi-square methods will be used to compare differences in treatment groups relative to placebo for the proportion of subjects with negative results on Day 3, Day 5 and Day 7 study visits.

A sensitivity analysis will also be performed; the data summary will be repeated in the mITT population excluding subjects who received antiviral therapy during the study. Determination of applicable antiviral therapy will be defined before the study is unblinded. All viral load data generated per the analytical plan will be listed.

For the influenza A virus subtype H3, virus load data measured by TCID₅₀ will be read out by both hemagglutination and NP-ELISA. The sensitivity is higher for NP-ELISA; therefore, all viral load parameters will be calculated using the data from NP-ELISA only.

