16 APPENDICIES

16.1 Changes to the Protocol Specified analyses

ADA data at Day 14 will not be analyzed.

Nasopharyngeal viral load samples will only be analyzed for qPCR and TCID₅₀ until Day 7, unless still positive on Day 7, and then samples will also be analyzed on Day 14. No PCR or TCID₅₀ samples are planned to be analyzed post-Day 14.

QTcF interval prolongation categories were updated to <450, >450 to ≤480, >480 to ≤500, and >500 msec and categories for QTcF increases were updated to <30, >30 to ≤60 and >60 msec from Baseline.

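### SAP 11.1 summarises H1 and H3 HAI titres over all mITT subjects whatever subtype infected them, and leaves the scheduled Day 14 titre without a summary or a declared change

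*SAP*

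**What the plan says.** SAP 11.1 sets the HAI summary: "Titer of anti-influenza A antibodies (H1 and H3 strains) will be summarized at Baseline/Day 1 and Day 28". The grouping is "by visit and treatment group for the mITT population". The statistics are n, mean, SD, geometric mean, CV, minimum and maximum. There is no breakdown by infecting subtype and no change from baseline. The mITT population (SAP 5.1.2) is treated subjects "confirmed influenza A positive by a molecular test at the central virological laboratory", so it admits any subtype.

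Protocol 9.3.6 plans immunology summaries by parameter, treatment group and time point, and gives one purpose as "HAI levels to determine a proper immune response to the influenza infection". In Protocol Table 1 and SAP 16.2, the row "Serum HAI sample" is marked at pre-dose, Day 14 and Day 28.

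SAP 16.1, which records changes to the protocol's analyses, says "ADA data at Day 14 will not be analyzed". It says nothing about Day 14 HAI.

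SAP 11.2, by contrast, summarises viral load "overall and per influenza A virus subtype". Subtype is a baseline variable in SAP 6.1, and Listing 16.2.8.7 gives virus type by subject.

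**The concern.** Two things looked wrong.

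- **Day 14.** A scheduled post-dose sample drops out of the summary with no declared change, in a SAP that does declare the same omission for ADA. The sponsor's own challenge study (Protocol 1.3, Table 3 footnote) used "HAI = hemagglutinin inhibition assay positive seroconversion at Day 14 or 28", so Day 14 has counted as informative for this assay in the programme.
- **Infecting subtype.** The protocol asks about the response to the infection. If infection with one subtype does not raise the titre to the other, each strain's mean over all mITT subjects combines people who could respond to that strain with people who could not. The summary then understates the response to the infecting virus and adds between-subject variance that has nothing to do with treatment.

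At stake is how well the trial serves one exploratory objective, the anti-influenza immune response. The primary safety conclusion is not involved.

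**Working it through.** The plan states no HAI effect size, subtype mix or power, so there is no figure of its own to reproduce.

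**Step 1: the schedule.** Each row of the assessments table has 13 time-point columns. The HAI marks fall in columns 3, 10 and 11: pre-dose, Day 14, Day 28. As a check on the count, the chemistry row read the same way gives Screening, Day 5, Day 14 and Day 100, which agrees with SAP 12.2. So SAP 11.1 covers one of two post-dose HAI time points.

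**Step 2: dilution.** The inputs below are assumptions, because the documents give none. Let p be the share of mITT subjects infected with the strain tested, F the geometric mean fold rise in those subjects, and 1 (no rise) the fold rise in the others. On the log scale the all-subject mean rise is p × log F, so the all-subject geometric mean fold rise is F^p.

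| Matched rise F | p = 0.25 | p = 0.5 | p = 0.75 | p = 0.9 |
|---|---|---|---|---|
| 4 | 1.41 | 2.00 | 2.83 | 3.48 |
| 8 | 1.68 | 2.83 | 4.76 | 6.50 |
| 16 | 2.00 | 4.00 | 8.00 | 12.13 |

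As p approaches 1, F^p approaches F and the dilution disappears for that strain.

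**Step 3: precision of an arm contrast.** Assume 50 per arm all in mITT, a matched rise of 3 log2, a true arm difference of 1 log2 in matched subjects, SD 1.5 log2 within each stratum, and two-sided 0.05. Over all subjects the difference shrinks to p × 1 and the SD grows to √(1.5² + p(1−p) × 3²). At p = 0.5 the difference is 0.5 and the SD is √(2.25 + 2.25) = 2.12. The matched-only contrast keeps the difference of 1 and the SD of 1.5, with 50p subjects per arm.

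| p | Power, all subjects | Power, matched only |
|---|---|---|
| 0.25 | 0.09 | 0.39 |
| 0.5 | 0.22 | 0.65 |
| 0.75 | 0.47 | 0.82 |
| 0.9 | 0.73 | 0.89 |

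SAP 11.1 plans no test, so these figures only express lost precision.

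**Step 4: imbalance in subtype mix.** With 50 per arm, the SE of the difference in share is √(2p(1−p)/50): 0.10 at p = 0.5 and 0.08 at p = 0.8. With F = 8 and p = 0.8, a one-SE imbalance gives a spurious ratio between arms of 8^0.08 = 1.18. Arms at 90% and 70% would read 8^0.9 = 6.50 and 8^0.7 = 4.29 with no true difference, but that gap is 0.20/0.08 = 2.5 SE and so unlikely.

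**Step 5: low titres.** SAP 11.1 says values below the limit of quantification are summarised as zero, and also that values under 10, which it labels the LLOQ, are taken as 5. A zero has no logarithm, so the geometric mean and any fold rise from such a baseline cannot be formed. The two rules conflict.

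**The case against.** The strongest reply is that only the Day 14 omission departs from the protocol. Protocol 9.3.6 does not ask for a subtype split, a fold rise or a seroconversion rate, and splitting viral load, a secondary endpoint, creates no duty to split an exploratory titre. The challenge-study footnote describes another trial and sets no standard here. All of that is fair. The split is a recommendation, resting on the protocol's stated purpose for HAI and on subtype data already held.

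It can also be said that the ratio of the Day 28 to the baseline geometric mean already gives the fold rise. That is true when the same subjects contribute at both visits. SAP 11.1 does not require this, and the zero rule can defeat it.

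Four stronger readings are tempting, and the documents do not support them:

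- **That H1 and H3 titres are combined with each other.** SAP 6.1 refers to both baseline titres as separate variables, and nothing in 11.1 merges them. What is pooled is subjects across infecting subtypes.
- **That the Day 14 results are discarded.** No text says the samples go unassayed, and Listing 16.2.8.19 (HAI, mITT) has no visit limit. What is missing is a summary.
- **That the trial sets out to learn whether VIS410 blunts or delays the antibody response.** The stated objective is only to assess that response.
- **That subtype mix biases the arm comparison.** Randomisation equalises the mix in expectation. What remains is attenuation and chance imbalance.

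**Conclusion.** The point holds, at minor priority. The Day 14 gap rests on the text alone: the sample is scheduled, a summary by time point is planned in the protocol, 11.1 leaves it out, and 16.1 is silent. The subtype point also rests on the text, since 11.1 has no analysis of the titre to the infecting strain.

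The size of the dilution cannot be computed from the documents. With no cross-strain rise and a matched share of 0.25 to 0.9, an 8-fold rise reads as 1.7- to 6.5-fold, a 4-fold rise as 1.4 to 3.5, and a 16-fold rise as 2.0 to 12.1. If one subtype accounts for nearly all infections, dilution is negligible for that strain and the Day 14 omission and the low-titre conflict are what remain. The endpoint is exploratory and descriptive, and the safety conclusions do not depend on it.

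**What to change.** In SAP 11.1 and Table 14.4.2.1:

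- Summarise HAI by strain and infecting subtype within each arm, with matched and unmatched rows. Show unsubtyped or mixed infections separately.
- Add the within-subject geometric mean fold rise from baseline, in subjects with both samples.
- Use one non-zero value for titres below the limit, in place of the present zero and 5.
- Add Day 14 to the summary, or declare and justify its omission in 16.1 as was done for ADA.

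A proportion with at least a 4-fold rise is optional; the documents set no such criterion for this trial.

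The cost is SAP and table-shell wording, plus reporting Day 14 from serum the schedule already collects. The downside is small cells for the less common subtype: at an assumed 80:20 mix and 50 per arm, 0.2 × 50 = 10 subjects per arm, to be read descriptively.

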11.2 Nasopharyngeal Viral Load

Standard non-compartmental approaches using Phoenix WinNonlin (Pharsight Corporation, Princeton, NJ, USA; Version 7.0 or higher) will be used to calculate peak viral load (VL) and the area under the viral load-time curve (VL AUC). Viral load at each study visit, proportion of subjects with negative results at each study visit, peak VL, and VL AUC based on qRT-PCR and TCID₅₀ from nasopharyngeal secretions will be summarized with n, mean, SD, geometric mean, CV, minimum and maximum values in the mITT population overall and per influenza A virus subtype. All available viral data within the mITT population will be assessed to calculate proportion of subjects with negative results at each study visit. For all other calculated parameters, viral load will be assessed on all samples in the mITT population collected through the Day 7 visit. In addition, VL and VL AUC for the first 50 subjects will be listed through Day 14 (no summary statistics will be presented). For missing data on Day 3, Day 5 and Day 7, the analysis will be conducted without imputation and with the last observable measurement carried forward (LOCF). For missing data on Day 1, the analysis will be conducted by replacing the missing data with the Day 3 observable measurement. Subjects missing both Day 1 and Day 3 virology data will be removed from the analysis.

A t-test will be used to assess the difference between treatment groups in the VL AUC and peak VL from nasopharyngeal swabs based on qRT-PCR and TCID₅₀. If the assumptions needed for the t-test are not met, log transformation and/or non-parametric methods will be used.

Chi-square methods will be used to compare differences in treatment groups relative to placebo for the proportion of subjects with negative results on Day 3, Day 5 and Day 7 study visits.

A sensitivity analysis will also be performed; the data summary will be repeated in the mITT population excluding subjects who received antiviral therapy during the study. Determination of applicable antiviral therapy will be defined before the study is unblinded. All viral load data generated per the analytical plan will be listed.

For the influenza A virus subtype H3, virus load data measured by TCID₅₀ will be read out by both hemagglutination and NP-ELISA. The sensitivity is higher for NP-ELISA; therefore, all viral load parameters will be calculated using the data from NP-ELISA only.

